5.2.4 SCREENING AND BASELINE EVALUATION

Potentially eligible patients will undergo an initial evaluation in which eligibility will be confirmed and the trial protocol explained in detail. All willing and eligible patients providing informed consent will have baseline data obtained including relevant history and use of all conventional and alternative therapies. Baseline laboratory tests will be performed and information on quality of life will be obtained.

The following variables will be obtained for all patients included in the trial: age, gender, weight, height, body mass index, blood pressure, left ventricular ejection fraction, hypertension, diabetes mellitus, peripheral vascular disease, medication use (angiotensin converting enzyme inhibitors, calcium channel blockers, beta blockers, statins, ascorbic acid, acetylcysteine, angiotensin receptor blockers, diuretics, aspirin), PCI (number of vessels) smoking status, amount of contrast, type of contrast, amount of hydration, serum hemoglobin, serum sodium, serum potassium, baseline creatinine and post procedure creatinine, glomerular filtration rate.

5.2.5 RANDOMIZATION

After inclusion and exclusion criteria verification, coordinator will complete the randomization screen, in the system. The patients will be randomly assigned to one of the two treatment arms. The coordinator will order the treatment in the patient's chart and start the pre-stocked infusion. The infusions will consist in intravenous nitroglycerin in addition to Intravenous Saline or Intravenous saline.

We will randomize using a computer generated pre-set list. The computer program will randomly assign a letter (A or B) to each individual case up to 400 cases. The trial coordinator and the pharmacist will be the only un-blinded persons that will have access to the randomization list. In case that for safety reasons an investigator must know if the patient is receiving the experimental therapy or not, a copy of the randomization list will be held at the coordinator's office.

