3.2 STUDY MANAGEMENT

The trial will be coordinated by the CoNaN Trial research teams that consist of the principal and co-principal investigators, sub-investigators, and a study coordinator. The study coordinator will evaluate eligibility; obtain consent, schedule subject's follow-up visits, data collection and maintenance of study documentation. Handling of investigational products will be the responsibility of an onsite pharmacist as well as the assistant investigators.

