5.2 STUDY POPULATION

5.2.1 PATIENT RECRUITMENT

The recruitment strategies for CoNaN trial are targeted to specific groups in order to meet study goals with respect to patient enrollment and demographics. Meeting these goals, which results in a study population that reflects the typical patient population with the disease/health characteristics of interest, is necessary for making informed conclusions based on data collected during the study.

CoNaN trial will randomize 400 patients with a Mehran score ≥ 6 in a 1 x 1 trial of intravenous nitroglycerin versus intravenous saline only. All patients must complete informed consent process prior to being randomized into the trial.

Patients will be recruited primarily from 2 different sites. (1) Mount Sinai Emergency department, once they are evaluated by cardiology and scheduled for a non-emergent catheterization. (2) Directly from the Mount Sinai Medical Center catheterization Laboratory.

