5.2.2 INCLUSION CRITERIA

All of the following inclusion criteria must be present for the patient to be enrolled in the trial.

- 1- Patient must be scheduled for percutaneous angiography, defined as diagnostic cardiac catheterization, or lower extremity or aortic iodinated contrast angiography.
- 2- Patients must have a Mehran score of at least 6 before the procedure.
- 3- Patients must have baseline creatinine and hemoglobin drawn before the procedure.
- 4- Signed informed consent.

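### The coordinator who judges eligibility and obtains consent can also read the pre-set A/B list, so the next assignment is not concealed from the person controlling trial entry

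*Combined protocol and SAP*

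**What the plan says.** On who controls entry, section 3.2 says: "The study coordinator will evaluate eligibility; obtain consent". The same section lists a single study coordinator in the research team. It also says: "Handling of investigational products will be the responsibility of an onsite pharmacist as well as the assistant investigators".

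On the allocation sequence, section 5.2.5 says: "We will randomize using a computer generated pre-set list" and "The computer program will randomly assign a letter (A or B) to each individual case up to 400 cases". On access: "The trial coordinator and the pharmacist will be the only un-blinded persons that will have access to the randomization list". It adds, for safety unblinding, that "a copy of the randomization list will be held at the" coordinator's office. The coordinator also completes the randomisation screen once the criteria have been verified, orders the allocated treatment and starts it.

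Two entry rules bear on this. Section 5.2.1: "All patients must complete informed consent process prior to being randomized into the trial". Section 5.2.2: "Patients must have a Mehran score of at least 6 before the procedure".

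No safeguard appears in the text available: no sealed envelopes, no list confined to pharmacy, and no release of one assignment at a time. The part of section 3.2 between its opening paragraph and 3.2.3 was not in the copy read and could not be checked.

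**The concern.** Randomisation protects the comparison only if whoever admits a patient cannot know which arm that patient would join. Here one role assesses eligibility, seeks consent, randomises, and may read the whole sequence beforehand. That person could delay, discourage or decline a patient according to the arm that comes next, perhaps without intending to. The arms would then differ at baseline for reasons unrelated to chance.

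Both the primary comparison (change in eGFR) and the CIN comparison would be exposed. Adjustment can address only measured factors. A trial already enrolled this way cannot be concealed afterwards, and with a single centre there are no other sites to dilute the effect.

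A related risk is conditional. If emergency unblinding means consulting the full list, or if investigators can see the A/B letters, unblinding one patient could reveal other patients' assignments. The text does not say how the lookup is done.

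**Working it through.** **The plan's own figure.** The point turns on no number in the plan. The nearest, 161 per arm in section 5.1, reproduces for 0.30 against 0.15, power 0.9, two-sided alpha 0.05, pooled variance and no continuity correction: [1.960 × √(2 × 0.225 × 0.775) + 1.282 × √(0.30 × 0.70 + 0.15 × 0.85)]² / 0.15² = 160.8, so 161. Nothing below changes it.

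**Roles side by side.**
- Judges eligibility and obtains consent: study coordinator (3.2).
- Completes the randomisation screen: coordinator (5.2.5).
- May read the list: trial coordinator and pharmacist, both described as unblinded (5.2.5).
- Copy of the list: coordinator's office (5.2.5).
- Orders and starts the infusion: coordinator (5.2.5).
- Screens again for exclusions, listed after the pre-procedure infusion: coordinator with assistant investigators (5.3, step 7). The text does not say whether failing this screen removes a patient.

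**Does the order of steps conceal the assignment?** No. Requiring consent and verification first would be enough if the assignment did not yet exist or could not be seen. Here it already exists and can be read.

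**Is there room for discretion?** Yes, in the consent conversation and in the Mehran score. The score must reach 6 before the procedure (5.2.2), but 4.2.1 counts contrast volume, and balloon pump use during or after the procedure. No assumed volume is given. From the points in 4.2.1:
- heart failure alone: 5
- diabetes with GFR 41–60: 3 + 2 = 5
- anaemia with GFR 41–60: 3 + 2 = 5

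Each becomes 6 if 100 cc of contrast is presumed, and stays at 5 if it is not.

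**Possible size (hypothetical; every input assumed).** Let half of candidates be high risk with CIN 30% and half lower risk with CIN 15%. Let the drug be inert, and let a fraction q of high-risk patients be passed over when nitroglycerin is next.
- High-risk share in that arm = 0.5(1 − q) / [0.5(1 − q) + 0.5]: 0.444 for q = 0.2; 0.412 for q = 0.3.
- Patients passed over to fill 200 places = 200 / (1 − 0.5q) − 200: 22 and 35.
- CIN in that arm = share × 0.30 + (1 − share) × 0.15: 21.7% and 21.2%, against 22.5% in the other arm. Relative risk 0.963 and 0.941; differences 0.83 and 1.32 percentage points.
- Type I error = Φ(−1.96 + δ) + Φ(−1.96 − δ), where δ is the difference divided by its pooled standard error. At 200 per arm, δ is 0.0083 / 0.0415 = 0.20 and 0.0132 / 0.0413 = 0.32, giving 0.055 and 0.062. At 161 per arm it is 0.054 and 0.060.
- For eGFR change, let the risk groups differ by d SD. Bias = (0.5 − share) × d, with standard error √(2/200) = 0.1 SD. For d = 0.2, q = 0.2: 0.011 SD and type I error 0.051. For d = 0.5, q = 0.3: 0.044 SD and 0.073.

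Stronger selection costs more. With a mean event rate of 0.30, 200 per arm and no drug effect, an assumed gap in underlying risk between arms of 2, 4 or 6 percentage points gives a rejection probability of 0.072, 0.141 or 0.258.

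**The case against.** The strongest reply has five parts.

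1. *The system may hide the next assignment, and the coordinator in 3.2 may not be the one in 5.2.5.* How the system releases assignments is indeed not described. But a hidden screen does not help when the same person has the full list. Only one study coordinator is listed, and 5.2.5 itself has the coordinator randomising straight after the criteria are verified. Nor does coding as A or B help, since the coordinator is described as unblinded and starts the infusion.

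2. *The coordinator is not the only gatekeeper.* This is correct. Under 5.2.1, cardiology evaluates emergency department patients and schedules them first. Trial eligibility and consent still rest with the coordinator under 3.2.

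3. *The Mehran ambiguity and the second exclusion screen are different problems.* This is largely fair. The first concerns how eligibility is defined, and many score items are fixed thresholds. The second concerns exclusion after randomisation. They show where judgement enters; the concealment failure stands without them.

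4. *The illustrated bias is small and assumed, and measured risk factors could be examined.* Both statements are true. Section 5.2.4 collects many baseline variables, though no adjusted analysis is stated. Selection in the opposite direction would, by symmetry, hide a benefit rather than create one. The example is therefore not evidence of severity. Imbalance in what was not recorded remains out of reach.

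5. *The missing part of 3.2 might hold a safeguard.* It could not be checked. Any safeguard there would contradict the access granted in 5.2.5, which would still need correcting.

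**Conclusion.** The concern holds, with high confidence, and should be corrected before enrolment. Followed as written, the plan lets the person who judges entry see the next assignment. That is a rule stated in the plan, not a missing detail. The conclusion assumes that the study coordinator and the trial coordinator are the same role, which is the natural reading.

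The size of any bias cannot be derived from the documents. Under the mild assumptions above, the type I error rises from 0.05 to between 0.055 and 0.062 for CIN, and to between 0.051 and 0.073 for eGFR change. Nothing in the documents suggests that the list would be misused. The point matters because concealment supports the causal reading of both comparisons and cannot be restored later.

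**What to change.** Amend sections 3.2 and 5.2.5 as follows.
- Only the pharmacist, who is already unblinded, holds the list. Remove the coordinator's access and the copy in the coordinator's office.
- The coordinator locks eligibility, including the Mehran items as scored before the procedure, and consent in the system. Only then does pharmacy release that one patient's assignment.
- Assistant investigators, who share product handling, receive only the infusion issued for that patient.
- Emergency unblinding uses a single-patient lookup or sealed code, held by pharmacy and reachable whenever an infusion is running.

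Sample size, endpoints and treatment do not change, and no new role is needed. The costs are the revised wording, single-patient codes and a short wait for release. Infusions that are now stocked in advance would have to be issued or labelled after release. Pharmacy must be covered during enrolment and while infusions run; its hours are not stated, so that cost is unknown.

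This change secures allocation concealment. It does not by itself blind whoever starts and titrates the infusion or collects safety data.

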5.3 STUDY ALGORythM

To achieve our primary and secondary end-points we will (1) screen patients in the catheterization lab and/or emergency department of Mount Sinai Medical Center. (2) After inclusion and exclusion criteria's are verified, informed consent will be signed by the patient. (3) a case report form will be completed. (4) The research staff will order a treatment protocol to be administered. (5) Laboratory studies will be performed if needed. (6) The patients will receive an intravenous infusion of nitroglycerin and/or saline for at least 1 hour. (7) Coronary angiography will be performed and another screening for exclusion criteria will be done by the coordinator and assistant investigators. (8) Variables such as volume of contrast and number of vessels stented will be obtained. (9) Patients will go to recovery area and another infusion will be started for another 3 hours. (10) 48 hours later patient will be contacted to come to the hospital for another set of laboratory studies or patients that stayed in the hospital will be contacted and all the information needed will be completed.

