4.1 PRIMARY ENDPOINT

The primary endpoint for this trial will be to determine the change in glomerular filtration rate after exposure to contrast media. We will compare the change in GFR before and after percutaneous angiography of the group that received intravenous nitroglycerin with the change in GFR before and after percutaneous angiography of the group that did not receive intravenous nitroglycerin.

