4.2 SECONDARY ENDPOINTS

Major secondary endpoints will include:

[figure not shown]
- 1- Incidence of CIN, defined as an increase in baseline serum creatinine of 25% or ≥ 0.5 mg/dl 48 to 72 hours post-percutaneous angiography
- 2- Safety profile of the interventions including volume overload, hypotension, headache, medication interaction, the need for hemodialysis, intra-aortic balloon pump, endotracheal intubation or the use of vasopressors.
- 3- Analysis and comparison to a CIN predictive score calculator (Mehran Score).

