4.3 SAMPLE AND METHODOLOGY

We will enroll 400 patients with a Mehran score of 6 or more that have a pre-procedural creatinine measured. Following baseline assessments, patients will be randomly assigned to receive intravenous infusion nitroglycerine plus intravenous normal saline or normal saline only.

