5.0 RESEARCH DESIGN AND METHODS

5.1 SAMPLE SIZE

NOT A CASE CONTROL STUDY. This is a randomized, placebo-controlled clinical trial with a 1:1 randomization of active therapy to placebo. Prior data from our retrospective study indicate that the failure rate among controls is 0.3. If the true relative risk of failure for experimental subjects relative to controls is 0.5, we will need to study 161 experimental subjects and 161 control subjects to be able to reject the null hypothesis that this relative risk equals 1 with probability (power) 0.9. The Type I error probability associated with this test of this null hypothesis is 0.05.

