5.2.3 EXCLUSION CRITERIA

None of the following exclusion criteria must be present for the patient to be enrolled in the trial

- 1- Patients on renal replacement therapy before randomization, will be excluded.
- 2- Being exposed to any types of nitrates 48 hours prior to randomization,
- 3- History of allergic reaction to any of the components of intravenous nitroglycerin.
- 4- Exposure to contrast media 4 days prior randomization.
- 5- Planned revascularization in the next 24 to 48 hours of the first PCI procedure.
- 6- The patient is hypotensive (<90/60mmHg) at the time of randomization.
- 7- Patients exposed to phosphodiesterase inhibitors 48 hours prior to randomization

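### Section 4.1 words the primary comparison by nitroglycerin received, and 5.3 repeats the exclusion screen after randomisation, but no section says that patients are analysed in their randomised arm

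*Combined protocol and SAP*

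**What the plan says.** Section 4.1 is the only place where the primary comparison is stated: "We will compare the change in GFR before and after percutaneous angiography of the group that received intravenous nitroglycerin" is set against the change "of the group that did not receive intravenous nitroglycerin". Section 4.3 describes the design by assignment: "patients will be randomly assigned to receive intravenous infusion nitroglycerine plus intravenous normal saline or normal saline only". The introduction (2.1) promises an analysis plan, but no analysis section follows, and no section defines an analysis set.

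Section 5.2.5 puts randomisation after the eligibility check and before the coordinator starts the infusion. It names the coordinator and the pharmacist as the only un-blinded people with access to the list. In 5.3 the infusion of at least one hour is step 6. At step 7, "Coronary angiography will be performed and another screening for exclusion criteria will be done by the coordinator and assistant investigators". Step 8 records contrast volume and vessels stented. Step 10 arranges laboratory tests 48 hours later. No consequence of failing the step 7 screen is given, for follow-up or for analysis.

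**The concern.** Taken literally, 4.1 groups patients by treatment received. An exclusion screen placed after randomisation, with no stated consequence, also leaves room to drop patients from the analysis. Either course would give up the protection of randomisation for the primary endpoint. In the second, one of the people running the screen knows the arm. Nothing in the text commits the trial to either course, but nothing rules them out, and the choice could be made after the data are seen.

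**Working it through.** **What can newly fail at step 7.** In 5.2.3, criteria 1, 2, 4, 6 and 7 are tied to randomisation, and criterion 3 is history. Criterion 5 is neither: "Planned revascularization in the next 24 to 48 hours of the first PCI procedure". It can first become known at the procedure, because 5.2.2 enrols patients for angiography "defined as diagnostic cardiac catheterization, or lower extremity or aortic iodinated contrast angiography" while step 8 of 5.3 expects stents.

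**Whether such patients are average.** A further procedure within 24 to 48 hours falls at or before the 48-hour sample of step 10. It may also fall before the CIN window, which 4.2 sets at "48 to 72 hours post-percutaneous angiography". The risk score in 4.2.1 adds one point per 100 cc of contrast. Their outcomes may therefore differ from average.

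**Size of a possible bias (illustration only).** The document gives no SD for eGFR change and no failure rate, so every share and every d below is assumed. Setting: inert drug, 200 per arm, arm mean 0, SD 1, affected patients d SD worse. SD is held at 1 after removal.

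- Removal of a share fa from the active arm and fc from control: shift = d × [fa/(1−fa) − fc/(1−fc)]; SE = √[1/(200(1−fa)) + 1/(200(1−fc))].
  - 5% v 5% or 10% v 10%: shift 0, error 5.0%; SE is 1.026 or 1.054 times as large.
  - d = 0.5, 10% v 8%: 0.5 × (0.1111 − 0.0870) = 0.012; SE 0.1048; error 5.15%.
  - d = 0.5, 10% v 5%: 0.5 × (0.1111 − 0.0526) = 0.029; SE 0.1040; error 5.9%.
- As-received regrouping of a share f of the active arm: shift = d × [f/(1−f) + f/(1+f)].
  - d = 0.5, f = 1%, 2%, 5%: shift 0.010, 0.020, 0.050; error 5.1%, 5.5%, 7.9%.
- d = 0: no shift. d = −0.5: the shifts change sign.

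**Cost of analysing as assigned.** The only sized comparison is CIN, a secondary endpoint. Section 5.1 has control risk 0.30, relative risk 0.5 (so 0.15), power 0.9 and error 0.05, and concludes "we will need to study 161 experimental subjects and 161 control subjects". Check, two-sided and without continuity correction: n = [1.960√(2 × 0.225 × 0.775) + 1.282√(0.30 × 0.70 + 0.15 × 0.85)]² / 0.15² = 160.8, so 161. The plan's figure is reproduced.

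At 200 per arm, let a share of the active arm go untreated at control risk:

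| Untreated (assumed) | Active-arm risk | Power |
|---|---|---|
| 0% | 0.150 | 95.1% |
| 5% | 0.15 + 0.05 × 0.15 = 0.1575 | 92.7% |
| 10% | 0.15 + 0.10 × 0.15 = 0.165 | 89.5% |

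**ANCOVA against the change score.** With equal variances σ² and correlation ρ between baseline and follow-up eGFR, the change score has variance 2σ²(1−ρ) and the ANCOVA residual σ²(1−ρ²). The ratio is (1+ρ)/2, which is 0.95, 0.90 and 0.85 for assumed ρ of 0.9, 0.8 and 0.7.

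**The case against.** *Received* is most naturally read as the arm. Section 4.3 randomises patients to receive one infusion or the other, 5.1 sizes experimental against control subjects under 1:1 randomisation, and 5.2.5 assigns two arms. A reader might infer from 4.1 that an as-treated analysis is planned; the rest of the document does not support that. Section 5.4 has the infusion started in the active arm without exception, so the share regrouped might be near zero.

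A reader might also infer that failing step 7 removes a patient. Section 5.3 does not say so: steps 8 to 10 carry on without exception, and 5.2.4 lists post-procedure creatinine among the variables for all included patients.

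A third inference is that nitroglycerin lowers pressure, so failures would pile up in the active arm. If 10% of that arm alone were dropped, with an assumed CIN risk of 0.40 to 0.60 against a true 0.30 in both arms, the error for CIN would be 5.6% to 11.0%. But the hypotension criterion in 5.2.3 applies at the time of randomisation, so a later fall in pressure does not meet it as written. For criterion 5, nothing suggests that an hour of infusion changes whether revascularisation is planned, and *planned* may mean planned at enrolment. Unequal removal would need the coordinator's knowledge of the arm to influence a screen shared with assistant investigators. That is possible but not shown.

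All of this stands, and it limits the point to a gap in the wording. It does not close the gap: a randomised design does not by itself say who is analysed, or in which group.

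**Conclusion.** The point holds in a narrow form. The one sentence that defines the primary comparison uses treatment received, an exclusion screen follows randomisation, and no section fixes the analysis set. The harm cannot be sized from the document. It is zero if affected patients have average outcomes, or if removal is alike in both arms. In the illustrations with d = 0.5 the two-sided error is 5.0% to 5.9% under removal and 5.1% to 7.9% under regrouping, on assumed shares throughout. Criterion 5 is the plausible route, and the contrast-volume points in 4.2.1 give some reason to think those patients are not average. The case for the change is that it closes an open choice on the primary endpoint cheaply, not that a bias has been shown.

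**What to change.** - **Section 4.1:** define the groups by randomised arm, state that all randomised patients are analysed as assigned, and keep an as-received comparison as a sensitivity analysis only.
- **Section 5.3:** state that the step 7 result does not change the analysis set. The follow-up creatinine is already planned in 5.2.4 and step 10. Any clinical role of that screen is for the investigators to reconcile with 5.2.3.
- **Separately, for precision and not as a bias correction:** compare arms by ANCOVA of post-procedure eGFR on treatment and baseline eGFR, which 5.2.4 already collects.

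The changes are wording and need no new data. The downside is slight dilution from untreated patients: for CIN, power at 200 per arm stays above the 90% asked for in 5.1 with 5% untreated and falls just below it with 10%. In addition, some retained patients may have had a second contrast exposure before the follow-up sample.
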